Smoking cessation: NRT and counseling. Smokers entering this study will be told that formal smoking cessation treatment will begin the day following Laboratory Session 2. At the end Laboratory Session 2, following the questionnaires and AB assessment, a master's level counselor will meet with the participant. The counselor will provide the participant with the first 4 weeks of an 8-week supply of NRT (NicoDerm CQ; GlaxoSmithKline, Research Triangle Park, NC), instruct the participant on the use of NRT, provide a smoking cessation treatment manual based on PHS guidelines (see the Appendix), and prepare the participant to quit smoking during a 30-minute counseling session. The participant will be educated and provided literature on the use and risks of nicotine patch use, and will be asked to begin using NRT and quit smoking the following day. Participants who complete at least one counseling call in this study will receive 8 weeks of NRT, consisting of 4 weeks of 21-mg patches, 2 weeks of 14-mg patches, and 2 weeks of 7-mg patches. The NRT treatment duration was chosen because meta-analysis suggests that there is little benefit of using NRT beyond 8 weeks [113]. During the 8 weeks of NRT use, participants will receive three biweekly 15-min counseling calls from the counselor (study days 29, 43, & 57; see **Figure 2**, above). Participants will be given a window of three days before and/or after the scheduled date of their phone counseling sessions to complete the session. During these phone sessions, the counselor will assess participants for medication changes, and patch and tobacco usage. At least two call attempts will be made during the course of the day however before the call will be considered missed. Missed phone sessions will be recorded in the study database but will not be logged as protocol deviations because they are expected in smoking cessation trials. After the last day of NRT use (study day 72), participants will return for their final laboratory session. Adverse events will be assessed throughout the study, and participants may choose to reduce or stop the NRT dosage in the unlikely event of dangerous or distressing adverse events. Our procedures for dispensing NRT, evaluating study compliance, and assessing adverse events follow standard FDA and clinical practice guidelines [114] and are well established in our research programs (e.g., [115,116]). Occasionally, research subjects may fail to utilize the NRT patch as instructed. In such cases, subjects will be instructed to mark the patch as missed in their smoking diaries and return the missed patch to the study team. Returned medications patches will be logged, stored in a locked file cabinet maintained by the study team, and will be destroyed per institutional guidelines. Missed patches and missed returns will not be logged as protocol deviations because they are expected in smoking cessation trials. In our previous trials about 75% of all participants take at least 80% of their intended patch use. Only adverse events related to use of the nicotine patch will be reported. The NRT and counseling component will be overseen by co-I [name], who has over 25 years of experience designing and conducting smoking cessation trials.

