Potential Risks. Nausea, vomiting, weakness, dizziness, and rapid heartbeat occur rarely and are most often caused by continuing to smoke while using the patch. If these reactions occur, and the participant is currently smoking and using the patch (i.e., the participant has lapsed but still is wearing the patch), participants will be counseled to reestablish a target quit day and gradually reduce their smoking rate. Participants will not be instructed to discontinue their patches if they have lapsed unless a serious adverse event has occurred, because research indicates that: 1) continuing patch use even when a lapse to smoking has occurred can increase the probability that recovery to abstinence will occur [125]; 2) high doses of nicotine, including 63-mg doses, do not lead to serious adverse events even with concurrent smoking [126]; and 3) patch use prior to a designated target quit day and with concurrent smoking does not lead to serious adverse events and can increase the chances for successful cessation [127]. Such findings have led to a general reconceptualization of the issue of concurrent tobacco and nicotine patch use in which smokers are now advised to continue nicotine patch use even if they have lapsed following a target quit day [128]. Some individuals who use the patch experience minor skin irritation, such as redness, rash, or minor swelling, and insomnia and dream abnormalities. Insomnia and dream abnormalities can be resolved by removing the patch during the night while sleeping. All of these reactions cease once the patch is removed. The EEG assessment carries the minor risk of skin irritation from the electrolytic solution, although this reaction is rare and easily treated. It is unlikely that completing the questionnaires, the attentional bias assessment, or the attentional bias modification task would lead to any potential risks for participants. In the event that an individual's response to a questionnaire indicates that there may be a mental health concern, staff will contact a mental health assessor and follow established procedures for handling mental health emergencies.

Table 1. Inclusion/Exclusion Criteria.

Inclusion Criteria

- Age: 18-65 year old.
- Smoking: an average of 5 or more cigarettes or little cigars per day prior to phone screen.
- Expired carbon monoxide (CO): ≥ 6 ppm or NicAlert >2.
- Having a working telephone.
- Seeking smoking cessation treatment.
- Fluency in spoken and written English.

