NRT is an FDA approved medication for smoking cessation. We will use an 8 week course of NRT as described in our methods. Moreover, we will also provide smoking cessation counseling consistent with the Clinical Practice Guidelines for Smoking Cessation.

The typical side effects of the nicotine patch are not usually serious in nature. Adverse effects will be assessed at each of the post-baseline laboratory and counseling sessions. In the event of a SAE being reported, a member of the medical team will be consulted. The SAE will be documented and reported according to institutional guidelines. The Tobacco Research & Treatment Program (TRTP) has trained medical personnel on staff that will be available to assist the PI and other personnel in managing medically related study issues.

Confidentiality will be protected by identifying subjects only by numbers in all data files. Identification numbers will only be connected to individual participant names in a separate file that will be accessible only by the PI and his staff. All study data files will be server-maintained with limited access by using passwords and logins restricted to study staff. All information will be reported in aggregate form, and individual participants will not be identified in any public reports or documents. We expect these procedures to be highly effective for protecting participant confidentiality.

3. Potential Benefits of the Proposed Research to Participants and Others

A primary benefit to participants in the proposed study is smoking cessation. All participants will receive empirically validated treatments for smoking cessation, concurrent NRT and smoking cessation counseling. We anticipate that many of them will continue to be non-smokers after the completion of the study. Smoking cessation is important in cancer prevention, cardiovascular events and emphysema rate reduction therefore reducing medical costs, and increasing well-being for both the participants and society in general. Smoking cessation is cost effective and results in a substantial reduction in healthcare costs for both the individual and society.

4. Importance of the Knowledge to Be Gained

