During the protocol review-and-approval process, the IRB determines the level of safety monitoring required for each protocol. The minimum monitoring requirements for low-risk trials include investigator monitoring of participant safety, AE reporting in compliance with IRB, NIH, and FDA guidelines, and participation in the Continuing Review process with the IRB. All other trials may also be monitored by the DMC. Outcomes of IRB and DMC reviews are conveyed to the PI via the administrative support staff in the Office of Protocol Research (OPR).

Guidelines for Filing Reports of Adverse Events at MD Anderson Cancer Center

We anticipate that when an AE occurs, it will be associated with NRT application site reactions, the most frequent adverse events associated with NRT. The use of the electrolytic solution for EEG collection might cause temporary skin rash in sensitive participants. Soon after removal of the EEG net, the skin redness disappears and does not result in serious adverse health consequences.

Adverse Events Requiring Prompt Reporting

Internal Serious Adverse Events (SAE) that are unexpected (not listed in the Informed Consent Document) and are related (possible, probable and definite) must be reported to the IRB within 5 working days. Deaths that are related and occur within 30 days after completion of treatment must be submitted to the IRB within 24 hours. Adverse events not meeting these criteria will be reported to the IRB at Continuing Review according to IRB policy.

Serious Adverse Event

A Serious Adverse Event is an event that meets one of the following: results in death, is life-threatening, results in hospitalization, results in persistent or significant disability/incapacity, results in a congenital anomaly/birth defect, based upon appropriate medical judgment, or may jeopardize the subject's health and may require medical or surgical intervention to prevent one of the other outcomes listed in this definition.

Data Quality and Integrity

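### The patch-only adverse event reporting sentence conflicts with the protocol's own safety sections, and no adverse event summary by randomised arm is planned

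*Combined protocol and SAP*

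**What the plan says.** The reporting sentence is in Section D, under the subsection on NRT and counseling: "Only adverse events related to use of the nicotine patch will be reported". It does not say to whom events are reported. Slightly earlier, the same paragraph says: "Adverse events will be assessed throughout the study".

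Section E has three further provisions:

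- Protection Against Risks: "Adverse effects will be assessed at each of the post-baseline laboratory and counseling sessions". On serious events it adds: "The SAE will be documented and reported according to institutional guidelines".
- Adverse Events Requiring Prompt Reporting, on the serious events it covers: "Internal Serious Adverse Events (SAE) that are unexpected (not listed in the Informed Consent Document) and are related (possible, probable and definite) must be reported". The recipient is the IRB and the deadline is 5 working days. For the rest: "Adverse events not meeting these criteria will be reported to the IRB at Continuing Review according to IRB policy".
- Guidelines for Filing Reports of Adverse Events, which anticipates an event unconnected with the patch: "The use of the electrolytic solution for EEG collection might cause temporary skin rash in sensitive participants".

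On the randomised intervention, Potential Risks says: "It is unlikely that completing the questionnaires, the attentional bias assessment, or the attentional bias modification task would lead to any potential risks for participants".

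Statistical Approach & Expected Outcomes, including the exploratory analyses and the power analysis, describes no adverse event table and no comparison of adverse events between arms.

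**The concern.** The sentence selects events by their relation to the one treatment that does not differ between the arms. What the trial randomises is the training, which is over before anyone wears a patch. A rule that passes only patch-related events therefore covers the background therapy and omits the experimental one.

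Two things are at stake. First, staff who follow the NRT subsection and staff who follow the monitoring plan would report different sets of events, and nothing in the document says which rule governs. Second, judging relatedness before an event is reported removes events ahead of any comparison. A between-arm comparison of harms is cleanest when all events are counted and relatedness is recorded alongside them. The protocol presents ABM as a possible adjunct to first-line therapy and argues that its benefits outweigh minor risks. Tabulated events from the trial would be the natural support for that statement.

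**Working it through.** No sample size, power or error-rate figure is involved. The check is a timeline and a comparison of sections.

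**Timeline** (nominal days from Figure 2, Study overview, and the NRT and counseling subsection)

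| Study day | Event | Can an event be patch-related? |
|---|---|---|
| 1 | Lab Session 1, with EEG | No |
| 2 to 14 | Training, ABM or sham: 14 − 2 + 1 = 13 days | No |
| 15 | Lab Session 2, with EEG; first post-baseline adverse event assessment; patches handed out | No |
| 16 | First patch use and quit day | Yes, from here on |
| 29, 43, 57 | Counseling calls, with adverse event assessment | Yes |
| 72 | Lab Session 3, with EEG | Yes |

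The visit windows move the dates but not the order, because the patch starts the day after Lab Session 2. All 13 training days and two of the three EEG sessions come before any patch use. With 250 participants, the planned training phase is 250 × 13 = 3,250 participant-days at full adherence, and no event on those days can meet a patch-relatedness test.

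**The rules side by side**

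| Event | NRT subsection sentence, read alone | Section E |
|---|---|---|
| Non-serious event during training | Not reported | Assessed on day 15; to the IRB at Continuing Review |
| Serious, unexpected event related to training | Not reported | To the IRB within 5 working days |
| Rash from the EEG solution | Not reported | Named as anticipated; to the IRB at Continuing Review |
| Non-patch event after day 16, such as a mood event during the quit attempt | Not reported | Assessed at calls and Lab Session 3; to the IRB at Continuing Review, or sooner if it meets the prompt-reporting criteria |
| Non-serious patch-related event | Reported | To the IRB at Continuing Review |

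The two rules agree only on the last of these rows. Assessment is not in dispute: both places have events assessed, and the day 15 visit captures the training phase before patch use.

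**Analysis.** The IRB route in Section E is an oversight route, not an analysis. Nothing in the statistical section converts the assessed events into a summary by arm, for any phase.

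**The case against.** The case for leaving the text alone has four parts.

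1. *Placement.* The sentence is in the NRT subsection, among text on missed and returned patches, and may be meant only for that component. This is plausible, but the same paragraph speaks of assessment across the whole study. Even if the rule is confined to the patch period, it still drops non-patch events from day 16 onward, which Section E would report.

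2. *The word reported is undefined.* If it means reported to the IRB, it contradicts Section E but does not stop the investigators comparing assessed events. If it means reported in the results, there is no conflict with the IRB rules, but published harms would be patch-only. This stands as a caution against claiming both consequences at once. Each reading still leaves something to correct.

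3. *Some psychological effects will be compared anyway.* The Exploratory Aims examine the impact of training type on withdrawal symptoms and mood states. That is true and useful, but scale scores are not adverse event data.

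4. *Low risk.* The protocol judges harm from the task unlikely. This limits the weight of the point. It does not settle which rule applies.

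A reader might go further and infer that no training-phase event could be reported or compared by arm, that there would be no harm data on ABM, or that every ABM-related event is excluded. The documents do not support this. Events are assessed throughout, including on day 15, and Section E gives serious and non-serious events a reporting route with no patch restriction. A comparison by arm remains possible; it is simply not planned. Nor do the documents show a deliberate choice to exclude harms of ABM.

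**Conclusion.** The point holds as an internal contradiction combined with an omission. The patch-only sentence cannot be followed together with the assessment and reporting provisions of Section E, and no adverse event summary by arm is specified. If the sentence were followed as written, events from all 13 training days, EEG reactions and other non-patch events would go unreported, and with them any difference in harms between ABM and sham.

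This rests on reading the sentence as applying to the study as a whole. On the narrower component reading, the conflict shrinks to non-patch events during the NRT period, while the missing by-arm summary remains.

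The number of events affected cannot be estimated, because the documents give no event rates. The practical weight is modest, given the low expected risk of the training, and the efficacy analyses are not affected. The correction is still worth making, because the rule filters harms through a treatment common to both arms and is cheap to repair.

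**What to change.** Reconcile the sentence in the NRT and counseling subsection with Protection Against Risks and the Data and Safety Monitoring Plan. Suggested replacement: all adverse events assessed at post-baseline visits and calls are recorded, with relatedness to the patch, the training and the EEG procedure held as a variable; events are summarised by randomised arm; reporting to the IRB follows the Data and Safety Monitoring Plan.

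Add one line to the statistical section specifying a descriptive table of adverse events by arm, split into events before first patch use and events from then on. No formal test is needed.

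The cost is one replaced sentence, slightly more recording and one extra table. Assessment at each post-baseline contact is already scheduled, so no visit or procedure is added and participant care does not change.

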The objective of this grant-funded proposal (R01CA184781) is to determine the feasibility of smartphone-delivered, in-home ABM to reduce AB to smoking cues and to reduce smoking behavior in the short- and long-term. Participants will be 250 treatment-seeking smokers, who will receive 8 weeks of nicotine replacement therapy (NRT) after completing either ABM (AB away from smoking cues and toward neutral cues) or sham training. Smokers will attend 3 sessions. The 1st lab session will establish each smoker's baseline smoking behavior and AB towards smoking picture and word cues by assessing reaction time (RT) and event-related potential (ERP) electroencephalography to modified dot-probe (MDP) and Stroop color-word naming tasks. After the 1st lab session, participants will complete 13 days of daily in-home training (ABM or sham), assessments to track changes in AB, and ratings of smoking behavior and craving, that will be administered through provided smartphones, with compliance and ABM accuracy rewarded monetarily. The 2nd lab session will occur immediately after the 2 weeks of in-home training and will involve the same assessments as the 1st session, to gauge the short-term impact of ABM on AB and smoking behavior. All participants will then receive counseling and the first half of an 8-week supply of NRT to quit smoking. The 3rd lab session, which will occur after NRT, will evaluate the longer-term impact of training on smoking behavior and AB. We propose the following specific aims and hypotheses that will address PQA3 of this RFA:

Aim 1: Identify the impact of in-home ABM on AB. We hypothesize that 2-wk in-home ABM, compared to sham training, will decrease AB towards smoking cues and increase AB towards neutral cues, as measured by RT to the MDP and Stroop tasks. We hypothesize that the changes in AB will generalize to novel and cross-modal stimuli. We hypothesize that short-term changes in AB will also be present at 8 weeks following the completion of training.

Aim 2: Identify the impact of in-home ABM on smoking behavior. We hypothesize that 2-wk in-home ABM, compared to sham training, will result in fewer cigarettes (including little cigars) smoked per day, lower expired carbon monoxide, lower urine cotinine values, decreased craving to smoke, and lower nicotine dependence after 8 weeks of NRT.

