
Statistical Approach & Expected Outcomes

Aim 1. Identify the impact of in-home ABM on AB. We will evaluate this aim using 2 (group: ABM vs. sham) X 3 (session: baseline, 1-day post-training, and 8-weeks post-training) linear mixed model using RT difference scores (neutral-cigarette) as the dependent measures and subject as the random effect. We will conduct separate analyses on the dependent measures (within-modality: MDP RT difference scores; between-modality: Stroop RT difference scores) collected at baseline, 1-day post-training, and 8-weeks post-training. We predict that post-training AB scores, calculated from RT, will decrease from baseline for those in the ABM training, but not in the sham training condition, indicating a reduction in AB to smoking cues.

Aim 2. Identify the impact of in-home ABM on smoking behavior. We will evaluate this aim using two types of models. For the continuous (i.e., normally distributed) measures of smoking behavior, we will conduct mixed between-within repeated measures ANOVA using the same predictors and covariates as are described in Aim 1. Separate analyses will be run for each of the continuous dependent measures, including mean CPD over the past 7 days, expired CO, cotinine, FTND, and WSWS Craving. We expect that ABM training, compared to sham training, will decrease measures of smoking exposure (CPD, expired CO, cotinine), levels of dependence (FTND), and levels of craving (WSWS Craving) at the 1-day and 8-weeks post-training sessions. For the categorical variable of 8-weeks post-NRT abstinence, we will conduct a chi-square test of independence on the 2 (abstinent vs. nonabstinent) x 2 (ABM vs. sham training) table. We expect that ABM training, compared to sham training, will result in a higher rate of abstinence.

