Exploratory analyses. We will examine the Aim 1 and 2 models covarying the total number of completed ABM or sham training sessions, the number of in-home training sessions completed, in-home training sessions accuracy rates, baseline FTCD, sex at birth, and CPD at each session. We will conduct the following exploratory analyses using multilevel modeling: (1) We will examine the impact of ABM on AB, CPD, and craving assessments collected by smartphone to determine whether the optimal length of training is less than 13 days; (2) We will examine whether individual differences, measured at baseline, predict response to the ABM training on our measures of AB and smoking behavior. These individual differences will include baseline levels of nicotine dependence (i.e., FTND, mCEQ, CPT, and WSWS), mood (i.e., PANAS), anhedonia (i.e., SLIPS), impulsivity (i.e., DDT, SUPPS-P), tolerance to stressors (i.e., DTS and ASI), reward sensitivity (i.e., Passive Picture Viewing), smoking exposure (i.e., CPD and expired CO), gender, handedness (i.e. Chapman Handedness questionnaire), and AB to smoking cues; (3) We will examine whether participants' contingency awareness of the ABM task influenced ABM's effectiveness, because one ABM study with smokers found that only those participants who were aware of the relationship between the probe and stimulus type were responsive to ABM [7]; (4) We will use data about the training environment collected using the smartphone (e.g., location, dB levels, ambient lighting) to examine whether these environmental characteristics influenced ABM's effectiveness; (5) We will use the EEG data collected using our 129-channel sensor net to perform event-related potential (ERP) analyses (including the P1 component), along with source localization analysis to attempt to identify areas in brain that are responsive to ABM. We will preliminarily target occipital regions that have been found to activate in the presence of motivationally salient visual cues [91,124]. (6) We will examine the effects of AB on eye-tracking metrics (e.g., fixation, gaze duration) and compare the reliability of eye tracking with traditional reaction time metrics of AB.

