Power analysis. To demonstrate that this proposal has adequate sample size to detect meaningful amplitude changes in the continuous measures taken at the post-training laboratory sessions (Specific Aims 1 & 2), we conducted a power analysis using the G*Power program (v3.1.2; Heinrich Heine University, Düsseldorf, Germany). We calculated power to ensure that we could detect a significant 2-way (ABM intervention by time) ANOVA interaction for any of our continuous measures, as assessed at the baseline, 1-day post-training, and 8-weeks post-training sessions. If we assume a conservative Bonferroni-corrected Type I error rate of $\alpha=0.01$, 250 participants, moderately correlated within-subject observations ($r=0.5$), and a conservative nonsphericity correction ($\varepsilon=0.75$) we have 80% power to detect differences corresponding to a Cohen's f of 0.11 or larger for the 2-way interaction. Even if we were to experience an unlikely 30% attrition rate, we would have power to detect a Cohen's f of 0.13 or larger. According to Cohen [117], a Cohen's f of 0.10, 0.25, and 0.40 correspond to a small, medium, and large effect size, respectively, meaning that we have the power to detect a small effect size or greater on our continuous measures. To demonstrate that we would have adequate power to detect likely AB differences for Aim 1, we searched the literature for studies with a similar design to ours. Given that no previous study has evaluated the impact of multi-session ABM on AB in

smokers, we decided to estimate a likely effect size from the one alcohol study that used the MDP task for both multi-session ABM and the AB assessments [2]. We estimated a Cohen's *f* value for this study by taking the square root of the *F* ratio multiplied by the ratio of the degrees of freedom [117]. From this formula, we estimated a Cohen's *f* of 0.64, based on the reported *F* value for the significant ABM training group (ABM, sham) main effect, $F(1,23)=9.4$, $p<.01$. This Cohen's *f* value corresponds to a large effect size and is well within the range for which we have sufficient power to detect. We recognize that this alcohol study does not provide an ideal comparison for the effects sizes we will likely obtain, but it does suggest that ABM produces large effects on AB, effects which should be well within the power requirements of our study to detect.

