In-home task compliance and accuracy. We expect high compliance and accuracy rates with the in-home ABM training and AB assessments. We were able to obtain compliance rates of 80% in a study in which we administered smoking cessation interventions and assessments with mobile phones to underserved persons living with HIV/AIDS, a high rate considering that many of them were homeless [56]. The only previous study to involve in-home ABM training, which was daily for 2 weeks, did not report a compliance rate, but did report an accuracy rate of 96% on the at-home ABM and AB MDP tasks [48]. Our ABM and AB tasks will have features designed to improve compliance and accuracy, including feedback after each block, and monetary incentives for task completion and accuracy. We will also have contingency procedures for contacting participants who do not comply with the in-home tasks, including email/texting and staff phone calls, if necessary. Compliance and accuracy rates will also be included in the statistical models used to evaluate our study aims.

[figure not shown]
AB assessment. The MDP and Stroop tasks that we are using to assess AB has been found to reliably detect AB across a variety of populations, including the healthy, the anxious, and the substance dependent. It has been found to be sensitive to multi-session ABM conducted with problem drinkers [29] and with the alcohol dependent [2,3]. Thus, we expect our AB tasks to be similarly reliable and sensitive to our ABM training. In terms of our exploratory ERP measure, the P1 ERP has been found to be a reliable indicator of AB in most [53,55,91] (but not all [118]) prior studies that evaluated P1 to a MDP task with motivationally relevant stimuli. However, if the P1 ERP is unable to distinguish AB, we would examine other ERP components, including the P2, N2, and the P3, all of which have been associated with later

stages of AB [118]. The P2 has been associated with attentional disengagement [119], the N2 with attentional control and inhibition [120], and the P3 with orienting of attention [121].

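### The continuous Aim 1 and Aim 2 models could gain power at no cost by adjusting for the outcome's own baseline instead of testing change from it

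*Combined protocol and SAP*

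**What the plan says.** Under Statistical Approach & Expected Outcomes, Aim 1 is analysed with a "2 (group: ABM vs. sham) X 3 (session: baseline, 1-day post-training, and 8-weeks post-training) linear mixed model" on reaction-time difference scores, with subject as the random effect. No covariate is listed. The continuous Aim 2 outcomes (cigarettes per day, expired CO, cotinine, FTND, WSWS Craving) get a repeated measures ANOVA "using the same predictors and covariates as are described in Aim 1".

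The Power analysis section identifies the test: it was sized to "detect a significant 2-way (ABM intervention by time) ANOVA interaction for any of our continuous measures", at alpha 0.01, 250 participants, r = 0.5 and a nonsphericity correction of 0.75.

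On timing, the Aim 2 hypothesis in the specific aims looks to the end of treatment, for example "lower nicotine dependence after 8 weeks of NRT". The Aim 2 analysis text expects benefit at both later visits, including lower "levels of craving (WSWS Craving) at the 1-day and 8-weeks post-training sessions".

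Baseline factors appear only under Exploratory analyses. One set of models adds training sessions completed and accuracy rates together with "baseline FTCD, sex at birth, and CPD at each session". Item (2) there reads "We will examine whether individual differences, measured at baseline, predict response to the ABM training on our measures of AB and smoking behavior". Separately, under Potential Problems & Alternative Strategies, the plan says "Compliance and accuracy rates will also be included in the statistical models used to evaluate our study aims". The Study overview states that randomisation is stratified by gender.

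**The concern.** When baseline is an outcome level with its own free arm difference, the interaction test spends information estimating a difference that randomisation makes zero in expectation. It also fixes the slope of post-training on baseline at 1, whatever the data show. Using the outcome's own baseline as a covariate, or constraining both arms to one baseline mean, avoids both. No main continuous model does this, although baseline is measured at the first laboratory session for every outcome.

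What is at stake is precision. For Aim 1, power is ample either way if the effect is near the f = 0.64 that the plan takes from an alcohol study. It matters more for smaller effects, and for the continuous Aim 2 outcomes, for which the Power analysis gives no expected effect.

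**Working it through.** **1. The plan's own figure.** Inputs from Power analysis: alpha 0.01, k = 2 arms, m = 3 sessions, r = 0.5, epsilon = 0.75. For a repeated-measures interaction, noncentrality = f² × N × m × epsilon / (1 − r), with df (k−1)(m−1) × epsilon and (N−k)(m−1) × epsilon.
- N = 250: df 1.5 and 372; 80% power at f = 0.1077 (plan: 0.11).
- N = 175 (30% attrition): df 1.5 and 259.5; 80% power at f = 0.1290 (plan: 0.13).

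Both reproduce.

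**2. Covariances of the two post-training arm contrasts.** Assumptions not in the documents: 1:1 allocation, compound symmetry (epsilon = 1), complete data. Take the baseline SD as 1, the post-training SD as s and the common correlation as r.
- Adjusted for baseline, A: diagonal s²(1 − r²), off-diagonal s²(r − r²).
- Change from baseline, C: every entry of A plus (1 − rs)².

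The added term is never negative. So adjustment never lowers the noncentrality relative to the interaction test with unstructured covariance; that is the only comparison for which this is claimed.

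**3. Equal variances (s = 1), r = 0.5.** A has 0.75 on the diagonal and 0.25 off it. Adding 0.5² = 0.25 gives C with 1.00 and 0.50. Noncentrality is proportional to d′V⁻¹d, where d is the vector of arm differences at the two post-training sessions and V is C or A.
- Effect at one session: C gives 1.00 / (1.00² − 0.50²) = 1.333; A gives 0.75 / (0.75² − 0.25²) = 1.500. Ratio 1.125.
- Equal effect at both: C gives 2 / (1.00 + 0.50) = 1.333; A gives 2 / (0.75 + 0.25) = 2.000. Ratio 1.50.

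**4. Power.** With 2 and 496 df at alpha 0.01, 80% power needs noncentrality 14.01. Multiplied by 1.125 it gives 85.6%; multiplied by 1.50 it gives 95.2%. Simulation of the 2-df multivariate tests (10,000 trials per cell) agrees: 79.4% to 85.0% (1-day effect), 79.5% to 85.1% (8-week effect), 79.7% to 95.1% (both). Both tests held their size near 1%.

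At f = 0.10, which the plan calls small, with N = 250 and epsilon = 1, noncentrality is 0.01 × 250 × 3 / 0.5 = 15.0 and power is 83.4%. Adjusted, it is 88.4% (one session) or 96.6% (both).

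**5. Range over r (s = 1).**

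| r | one session | both sessions |
|---|---|---|
| 0.3 | +22% | +88% |
| 0.5 | +12.5% | +50% |
| 0.7 | +6% | +25% |

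**6. Unequal SDs (r = 0.5).** With s = 1.5, A has 1.6875 and 0.5625; adding (1 − 0.75)² = 0.0625 gives C with 1.75 and 0.625.
- One session: A gives 1.6875 / 2.5313 = 0.6667, C gives 1.75 / 2.6719 = 0.6550; ratio 1.018.
- Both: A gives 2 / 2.25 = 0.889, C gives 2 / 2.375 = 0.842; ratio 1.056.

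With s = 2, rs = 1, the added term is zero and there is no gain. With s below 1 the gain exceeds step 3.

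**7. Covariance structure.** A subject random effect alone implies compound symmetry, whereas the power calculation allows epsilon = 0.75. Three correlation patterns were assumed (baseline–1-day, baseline–8-week, 1-day–8-week): (0.7, 0.2, 0.6), (0.8, 0.35, 0.35) and (0.35, 0.35, 0.8), with epsilon 0.73 to 0.74. Under each, an F-test that takes compound symmetry as true and is not corrected rejects about 2% of the time at nominal 1% (40,000 null trials each).

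**The case against.** The strongest reply is that this is a preference. The planned contrast is unbiased, it matches a hypothesis worded as a decrease from baseline, and it is the test that was powered. That stands, and it caps the point at an optional improvement.

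A second reply is that the size of the gain rests on things the documents do not state. That also stands. Smoking measures after a quit attempt need not keep their baseline SD, and step 6 shows that the gain can vanish. Nor can the percentages be carried over to the epsilon-corrected ANOVA: with unequal correlations, that test and the adjusted unstructured test differ in ways the ratios above do not capture. No power range is therefore given for epsilon = 0.75.

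Three stronger readings are tempting, and the documents do not support them.
- **The planned analysis is biased or has inflated type I error.** The between-arm interaction is unbiased under randomisation. The 2% in step 7 applies only to an uncorrected compound-symmetry test under assumed correlations. The plan does not say that its test will be uncorrected, and its power calculation includes a correction.
- **The trial is underpowered.** The stated detectable effects reproduce. The sample size stands.
- **The main models condition on compliance and accuracy.** The sentence "Compliance and accuracy rates will also be included in the statistical models used to evaluate our study aims" could be read that way. But Exploratory analyses describes the Aim 1 and Aim 2 models with exactly such covariates, and the sentence is naturally read as referring to those. A clarification is enough.

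**Conclusion.** The point holds as a free improvement in efficiency for the continuous outcomes only. At the plan's r = 0.5, and on the assumptions in steps 2 and 3, noncentrality rises by 12.5% to 50% and 80% power becomes about 86% to 95%, depending on whether the effect is at one post-training session or equal at both. The plan's texts point both ways on that: the Aim 2 hypothesis stresses the end of nicotine replacement, while the analysis section expects effects at both visits.

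Confidence is high in the direction and moderate at best in the size, because no outcome SDs or observed correlations are given. The abstinence chi-square test is not affected.

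**What to change.** In the main continuous models for both aims:
- Constrain the two arms to a common baseline mean. Alternatively, use the outcome's own baseline as a covariate with the two post-training sessions as outcomes; with complete data the two are in effect the same. Do not use baseline as both outcome and covariate.
- Include gender, the stratification factor.
- Use an unstructured covariance over sessions in place of a subject random effect alone.
- Name one joint 2-df arm test over the 1-day and 8-week sessions per outcome, so that the number of tests does not change.
- Keep sessions completed, accuracy and cigarettes per day at each session out of these models, and state that compliance and accuracy enter only the exploratory ones.

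The cost is a short rewording, fixed before outcome data are analysed by arm. The continuous Aim 2 outcomes move from repeated measures ANOVA to a mixed model of the kind already planned for Aim 1. No new data, visits or participants are needed.
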